6.0 Study Procedures

Encounter 1: Enrollment and Informed Consent

• Performed by study nurse in VU outpatient clinic or inpatient setting

Encounter 2: Day of AF Ablation

- Ablation will be scheduled by the patient's physician according to clinical availability and is often offset by 1-60+ days from time of enrollment. The scheduling of the AF ablation procedure and post-procedure care are determined by the availability of the operator and patient according to standard of care practices.
- AF ablation will be performed according to standard of care practice by the patient's physician. Table 3 summarizes an estimated time frame for the clinical activities and simultaneous performance of the study protocol
- After the patient arrives in the operating room, they will be undergo standard of care preparation for surgery including sterile drape and administration of general anesthesia using endotracheal intubation and mechanical ventilation.
- A transesophageal echocardiogram (TEE) is performed as standard clinical practice by the cardiac anesthesiolgy attending physician immediately following intubation. This is performed to exclude the presence of a left atrial appendage thrombus and to document the presence of any pericardial fluid at baseline. The TEE is then used later in the procedure to assist in visualization of the interatrial septum for transseptal puncture. As part of the research protocol TEE pictures of the LV will be recorded to allow for offline measurement of LV contractility.
- "Time out" will be performed at the start of the case by the primary operator. Immediately following timeout, the study drug infusion will be started (1 mg/kg over 10 minutes; maximum dose 100 mg).
- 15 minutes following completion of the study drug infusion, blood will be collected from central venous sheaths that are placed at the beginning of the case. Blood will be drawn from the sheaths immediately before the AF induction protocol. This will be to enable measurement of serum propafenone levels at the time of AF induction testing. Blood will be delivered to the core laboratory for Cardiovascular Translational and Clinical Research for DNA extraction and serum/plasma storage.
- Next, repeat TEE recordings of the LV will be performed.
- The AF ablation procedure will be performed as per standard of care by the primary operator and clinical team. [name] and a study nurse will perform the study protocol.
- A standard electrophysiologic (EP) study will be performed at the start of the case after intracardiac catheter placement (including a decapolar CS catheter). The standard clinical EP study includes

measurement of AV block cycle length, AV node effective refractory period (ERP), atrial ERP, and ventricular block cycle length. Diastolic pacing threshold will be determined, and AERP will be tested at a pacing output of 2 times the diastolic threshold at 2 ms (standard of care). Following measurement of these conduction intervals, the pacing protocol to test for AF inducibility will be performed as follows:

- Stimulation Protocol #1:
 - A standardized protocol will be used to induce AF or atrial flutter (AFL).
 - This protocol is similar to common clinically used protocols to induce supraventricular tachyarrhythmias during performance of clinical EP studies.
 - The LA will be paced from the most distal CS electrode that can consistently capture the atrium. The CS catheter will be placed in standard clinical position.
 - o 15 beat bursts of 20mA amplitude and pulse width of 2 msec will be used
 - We will wait 10 seconds between bursts and decrement by 10msec for each burst
 - Step 1: starting cycle length will be 250 msec and decrement down to 180 msec or loss of 1:1 atrial capture (AERP). If there is no 1:1 capture at 250ms, the starting cycle length will be 10ms greater than the coupling interval of the atrial ERP at a drive train of 600 ms.
 - Step 2 will be used if there is no sustained AF/AFL during Step 1, and it will consist of 5 atrial pacing bursts of 15 seconds at the lowest cycle length of which 1:1 atrial capture was achieved.
 - The parameters for this AF induction pacing protocol can be programmed into the cardiac stimulator system (EP-4 Cardiac Stimulator, St. Jude Medical Inc., St. Paul, MN) and performed automatically. The time required to perform Step 1 of the research pacing protocol is ≤ 96 seconds, and Step 2 (conditional on step 1 being non-inducible) is ≤ 125 seconds.
 - Sustained AF/AFL will be defined by a duration of >30 seconds.
 - Patients who develop sustained AF/AFL will either: 1) spontaneously convert prior to ablation; 2) convert during the ablation procedure (majority of patients); or 3) undergo direct current cardioversion (DCCV) at the end of the case. DCCV during AF ablation procedures is common and will be performed according to standard clinical practice at the discretion of the attending physician.
 - Some patients will develop AF/AFL during the standard clinical EP study. If it sustains >30 seconds it will be counted toward the primary endpoint, and the research AF induction pacing protocol will not be performed.
 - Standard-of-care monitoring following an AF ablation is inpatient 23-hour continuous cardiac telemetry observation with specialized cardiac-trained nursing care. Cardiac-trained nurse practioners remain in the hospital overnight and communicate with the electrophysiology fellow on call at night for any patient care issues. Intravenous access is maintained post-procedure during their hospitalization.

7.0 Risks

Patients undergoing AF ablation are at risk for complications by nature of the procedure. These risks are inherent to the patient population studied here. The risks of obtaining blood samples from existing venous lines and determination of serum propafenone levels are minimal. There are risks associated with inducing atrial fibrillation and D/C cardioversion, however these are commonplace during AF ablation and add little to the risk inherent to this study population. There are risks associated with propafenone which include: new or worsened arrhythmias, unmasking Brugada syndrome, new or worsened congestive heart failure, conduction disturbances, altered pacemaker thresholds, agranulocytosis, exacerbation of myasthenia gravis, elevated ANA titers, and impaired spermatogenesis. Proarrhythmic effects may be more pronounced in patients with patients with liver or kidney disease, or patients taking other QT-prolonging drugs or inhibitors of CYP2D6, CYP3A4, and CYP1A2 isoenzymes. The majority of these risks are associated with chronic use, and are less applicable to the single dose regimen used for this study. Furthermore, the potential arrhythmic adverse effects are easily treated in the setting of the EP lab. There may be unknown risks of R- and S- propafenone, although these specific enantiomers have been previously used in clinical studies, both orally and as a single IV dose as we propose.

Major side effects of propafenone include bradycardia and proarrhythmia. We will monitor for these side effects with continuous cardiac telemetry. Patients are admitted for 23-hour observation following atrial fibrillation ablation. Propafenone will no longer be biologically active prior to discharge in the majority of

patients. In a small subset of patients who are poor metabolizers, duration of action may extend to 32 hours, however the peak effect will have been observed prior to discharge. At the discretion of the attending cardiac electrophysiologist, the decision will be made to withhold discharge in the case of unresolved symptomatic bradycardia or ventricular ectopy believed to compromise patient safety.

One risk of donating samples for genetic research may be the release of information that could link the patient to the stored samples and/or the results of the tests run on those samples. The release of this information could cause problems with insurance or future employment. We have mechanisms in place to protect against such risks.

A serious adverse event/experience (SAE) or reaction is any untoward medical occurrence that at any dose:

- 1. results in death
- 2. is life-threatening
- 3. requires inpatient hospitalization or prolongation of existing hospitalization
- 4. results in persistent or significant disability/ incapacity (as per reporter's opinion)

- 5. is a congenital anomaly/birth defect
- 6. is another medically important condition
- 7. The term "life-threatening" in the definition of "serious" refers to an event in which the patient is at risk of death at the time of the event; it does not refer to an event which hypothetically might have caused death if it were more severe.

Important medical conditions that may not result in death, be life-threatening, or require hospitalization may be considered as SAEs when, based upon appropriate medical judgment, they may jeopardize the patient or may require intervention to prevent one of the outcomes listed in the definition above. Examples of such events are intensive treatment in an emergency room or at home for allergic bronchospasm; blood dyscrasias or convulsions that do not result in hospitalization; or development of drug dependency or drug abuse.

Definition of severity of adverse events:

- Mild: Causing no limitation of usual activities; the subject / patient may experience slight discomfort.
- Moderate: Causing some limitation of usual activities; the subject / patient may experience annoying discomfort.
- Severe: Causing inability to carry out usual activities; the subject / patient may experience intolerable comfort or pain.

Definition of adverse event causality:

The Investigator will determine causality of each adverse event by using the classification criteria: unlikely, likely, or not assessable.

- *Unlikely:* The AE is considered by the Investigator to be due to a pre-existing condition, a known manifestation of the target disease, a recurrent condition, or is likely explained by environmental or diagnostic therapeutic factors or was pre-existing and did not deteriorate.
- *Likely:* The AE occurred during or after administration of the study treatment or a pre-existing event worsened within an appropriate period of time, and at least one of the following criteria is applicable:
 - the event could not be explained by the clinical condition or history of the subject, environmental or toxic factors, or other diagnostic or therapeutic measure;
 - o was an expected ADR associated with study treatment or a class-labeled drug effect;
 - o AE subsided or disappeared after withdrawal or dose reduction of study treatment; or
 - AE recurred after re-exposure to study treatment.
- *Not assessable:* There is insufficient or conflicting evidence for classifying the causality of the AE as likely or unlikely. Lack of information may apply for this situation.

Note: AEs with causality 'likely' or 'not assessable' are considered to be 'possibly drug-related.'

Adverse event reporting

Any adverse events (AEs) will be reported to the PI within 72 hours of notification of the event. The PI will notify the DSMB of any major adverse events. Any unanticipated problems involving risk to the participants or others will be discussed with the PI and DSMB. Non-serious AEs and incidences of noncompliance with the protocol will be reported to the IRB at the time of annual review.

Serious Adverse Events (SAEs) will be reported according to the following procedure:

The occurrence of serious adverse events will be reported to the Investigator within 24 hours after notification of their occurrence. The Investigator will report SAEs to the DSMB and Vanderbilt Institutional Review Board within 7 days of the Investigator's notification of the event.

In an unanticipated event of prolonged side effect, requiring prolongation of hospital stay, patients will be retained in the hospital until side effects have resolved. For minor side effects, where inpatient care is deemed unnecessary, follow- up will be maintained via phone or as outpatient if necessary. Patient and their families will be given the PI's contact number for reporting any other effects of medication following discharge.

Any newly discovered information which may affect the subject or their caregiver's decision to continue to participate in the study will be passed on to them as soon as possible. This may also result in a change to the consent form and review by the IRB.

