5.0 Enrollment/Randomization

Recruitment and informed consent: Eligible subjects will be identified through StarPanel. A member of the study team will request an introduction from the clinical staff, if the patient agrees. Following the introduction, the team member will approach the patient prior to AF ablation. Information describing the study, why the research is being done and what will be learned will be provided. The risks as described above will be delineated. The benefits will be described as general scientific knowledge, along with potential treatment advances. No direct immediate benefit to the subjects is anticipated. Informed consent will be documented with the subject's signature using an IRB-approved consent form for this protocol.

Randomization: This will be a double-blind, randomized study. Eligible subjects will be randomized according to a permuted block scheme with a block size of balancing interval, varying randomly according to the outcome of a computer-generated random number. This ensures that the cumulative number of assignments to each treatment (R-propafenone, S-propafenone, or placebo/vehicle) will be in balance after each block of assignments had been made. A statistician will design the randomization table and enable the randomization tool within REDCap. After a patient enrolls for the study, the study nurse will determine the treatment assignment using the randomization tool in REDCap. The day prior to the ablation procedure, the study nurse will notify IDS to prepare the study drug. The morning of the AF ablation procedure, the study nurse will pick up the study drug from the IDS.

An initial set of 6 patients received (R)- or (S)-propatenone at a rate of 1mg/kg to establish subject safety. This was open-label and not randomized. The data was reviewed with the DSMB on Dec 1, 2016. The DSMB recommended continuing the study with the 1mg/kg dose.

The study drug will be administered via a peripheral i.v. at a rate of 1mg/kg (maximum of 100mg) over 10 minutes. This will occur following induction of general anesthesia at the start of the procedure (Table 3). [name] will remain blinded to the treatment assignment as he is responsible for performing the study pacing protocol, electrogram interpretation, and interval measurement.

Table 3. Time Table for Study Protocol During AF Ablation

Time Elapsed (hrs:mins)	Standard of Care Activities	Research-only Activities
0:00→0:45	General anesthesia + TEE	

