0:45→0:55	Sterile Prep and Drape	
0:55→1:00	 Operator Scrubs Official Time-out 	Study Drug Infusion Starts (0:55)
1:00→1:10	Venous Sheaths Placed	Study Drug Infusion Ends (1:05)
1:10→1:20	CS Catheter Placed	
1:20→1:25		 Blood Sample Drawn + TEE EP Study (AVNERP, AERP) Rapid Atrial Pacing Protocol 1° Endpoint Determined End of Research Protocol
1:25→end	AF ablation proceeds according to standard of care procedures	

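### The only AE severity scale relies on usual activities and felt discomfort, so it cannot grade non-serious events that start and resolve under general anaesthesia, when the drug is given and assessed

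*Combined protocol and SAP*

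**What the plan says.** Section 8.0, under the definition of severity, gives three grades. The lowest is worded "Mild: Causing no limitation of usual activities; the subject / patient may experience slight discomfort". The middle grade has the same two parts, with partial restriction of activity and a greater degree of discomfort. At the top of the scale the wording is "Severe: Causing inability to carry out usual activities; the subject / patient may experience intolerable comfort or pain" (the word comfort in this grade is apparently a slip for discomfort).

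No other severity scale appears, and no grade refers to ECG findings, haemodynamics or need for intervention.

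On the timing of the study drug, section 5.0 says: "This will occur following induction of general anesthesia at the start of the procedure". Section 6.0 describes the preparation as including "administration of general anesthesia using endotracheal intubation and mechanical ventilation". Table 3 in section 5.0 sets out an estimated clock for the infusion and the research assessments.

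On reporting, section 8.0 also says: "The PI will notify the DSMB of any major adverse events". It does not define major.

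**The concern.** Each grade asks what the patient can do or feels. An anaesthetised, ventilated patient has no usual activities to limit and cannot report discomfort. The drug risks that section 7.0 singles out, bradycardia and proarrhythmia, are seen on a monitor and not reported by the patient. The same section says that arrhythmic effects are easily treated in the EP laboratory, so an event could begin, be treated and end before the patient wakes. The scale would have nothing to register.

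What is at stake is the meaning of the severity grade for these events. A block that needed treatment and a brief slowing that needed none could carry the same grade, or no grade. Section 7.0 accepts that the separate enantiomers may carry unknown risks, so intraoperative safety data should be interpretable.

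**Working it through.** No sample-size, power or alpha calculation applies. The check sets the timing beside the grading rule, then asks where the grade is used.

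**1. Timing (Table 3, section 5.0; section 6.0)**

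| Step | Clock | Interval |
|---|---|---|
| General anaesthesia and TEE | 0:00 to 0:45 | |
| Study drug infusion | 0:55 to 1:05 | 10 min |
| Infusion end to the block with blood draw, TEE, EP study and pacing | 1:05 to 1:20 | 15 min |
| That block, to end of research protocol | 1:20 to 1:25 | 5 min |
| Ablation | from 1:25 | |

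The 10-minute infusion and the 15-minute wait agree with the text of section 6.0. The research period runs 30 minutes from infusion start (1:25 − 0:55) and 20 minutes from infusion end (1:25 − 1:05). All of it falls after induction and before the ablation.

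**2. The grading rule applied to three kinds of event**

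- *Non-serious, starts and resolves under anaesthesia.* Take a transient block that is treated. It limits no usual activity, which is the Mild criterion. The discomfort clause says only what the patient may feel, so the absence of reported discomfort does not exclude Mild. A grader who thinks the criteria do not apply has no other grade to use. The result is Mild or no grade.
- *Persists, or has consequences, after waking.* The scale works. Section 7.0 provides 23-hour observation after the ablation.
- *Serious.* Seriousness is defined separately in section 8.0. It covers life-threatening and medically important events, including those that may need intervention to prevent a listed outcome. None of this depends on the severity grade.

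**3. Where the grade is used**

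- SAEs go to the investigator within 24 hours, and from the investigator to the DSMB and IRB within 7 days, on seriousness.
- All AEs go to the PI within 72 hours; non-serious AEs go to the IRB at annual review. Neither rule refers to severity.
- The DSMB reviews adverse events and drug reactions no less than two times a year, with no severity filter.
- An unexpected drug reaction is judged on nature or severity against product information, not against these grades.
- Section 10.0 contains no safety analysis.
- Major, the trigger for PI notice to the DSMB, is neither defined nor linked to the scale.

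The first kind of event in step 2 is therefore the only one that the scale fails, and no reporting duty or planned analysis depends on the grade it gives.

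**The case against.** The strongest reply is that the grade does no work in this plan. Reporting follows seriousness, which can be judged in an anaesthetised patient; the DSMB sees all adverse events regardless of grade; and the plan has no AE table or between-arm comparison by severity. All of that stands, and it limits the point to the quality of the severity data.

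Three stronger readings are tempting and should not be drawn.

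- *Every intraoperative event is Severe because the patient can do nothing.* The wording requires the event to cause the inability. Here the anaesthetic causes it. The failure is under-grading or no applicable grade, not a swing from lowest to highest.
- *The arms cannot be compared on safety.* AE and SAE counts by arm remain available, and events that outlast anaesthesia can be graded. The documents plan no comparison by grade.
- *The DSMB would not hear of these events.* This needs major to be read through the severity scale, and nothing in section 8.0 makes that link. Section 7.0 uses the same adjective for bradycardia and proarrhythmia, which points towards notice of such events. Periodic DSMB review covers them in any case.

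The reply does not supply a criterion. If severity is to be recorded, no text says how to grade an event that is over before the patient wakes.

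**Conclusion.** The point holds in a limited form. For non-serious adverse events that start and resolve under anaesthesia, the stated scale gives Mild or gives no grade, so severity data on those events would be uninformative to the DSMB. The gap covers the infusion and all on-drug research assessments, and continues until the patient wakes. It applies to all arms of the planned 243 patients (108, 108 and 27). How many events fall in it cannot be calculated, because the documents give no rate.

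SAE capture, AE counts, the efficacy analysis and the grading of events that persist after waking are not affected.

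Two assumptions are made. First, anaesthesia continues through the ablation; Table 3 does not state the time of waking. Second, graders apply the scale as written; the documents do not say how they would act in practice. The absence of an applicable criterion does not depend on the second assumption. The change is worth making because it is cheap and the gap coincides with the on-drug research period.

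**What to change.** In section 8.0, add a severity scale for adverse events with onset under anaesthesia, based on observable effect and response. One possible layout is:

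- lowest grade: no intervention;
- middle grade: intervention given and the procedure continued;
- highest grade: procedure interrupted or stopped, or the event was life-threatening.

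The investigators should set the exact clinical content. Keep the existing scale for use after recovery, and record the worst grade for an event that spans both periods. Correct the apparent slip in the Severe definition.

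Do not define major as Severe or SAE only. Under the layout above, a block that is paced while the procedure continues would take the middle grade. If it were not an SAE, it would then fall outside PI notice to the DSMB. Any definition of major in section 8.0 should be reconciled with section 7.0, which names bradycardia and proarrhythmia as the major side effects.

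The cost is a wording change and, assuming a conventional AE form (the documents do not show it), one extra option. Some events will take a higher grade than under the present scale. Grades will also depend partly on the clinician's decision to intervene, so the criteria need to be worded for consistent use across arms.

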9.0 Study Withdrawal/Discontinuation

Participants may withdraw from the study at any time by informing the study staff verbally or in writing. If an individual withdraws their consent, we will withdraw the participant. Contact information for the PI and study staff will be made available to the participant upon enrollment in the consent document. Any remaining biological samples and data will be destroyed. Any data or biological samples that have been used for research prior to their withdrawal request will not be withdrawn and destroyed.

A participant may be withdrawn from the study by the PI if any of the following occurs:

- i. A procedural complication occurs prior to completion of the study protocol that requires the AF ablation procedure to be aborted, or precludes collection of study data.
- ii. The patient becomes hemodynamically unstable for any other reason that requires the AF ablation procedure to be cancelled prior to completion of the study protocol, or precludes the collection of study data
- iii. The primary operator determines it is in the patient's best interest to forego completion of the study protocol
- iv. The patient spontaneously converts to AF or atrial tachycardia/flutter prior to completion of study protocol

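### Withdrawal rule iv lets dosed patients leave because AF appears before testing, and the plan does not say how that AF, or AF during the EP study, enters the primary analysis

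*Combined protocol and SAP*

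**What the plan says.** Section 9.0 opens its list of PI withdrawals with "A participant may be withdrawn from the study by the PI if any of the following occurs". Item iv on that list is "The patient spontaneously converts to AF or atrial tachycardia/flutter prior to completion of study protocol". The rule sets no lower time limit, so it covers patients already randomized and dosed. The sentence "Any remaining biological samples and data will be destroyed" stands in the preceding paragraph, on participants who withdraw consent.

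Table 3 (section 5.0, estimated times) starts the infusion at 0:55, ends it at 1:05, and puts the blood sample, TEE, EP study and pacing protocol in the 1:20 to 1:25 slot. Section 6.0 agrees on the wait: "15 minutes following completion of the study drug infusion, blood will be collected from central venous sheaths".

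Section 6.0 has one rule for AF before the pacing protocol: "Some patients will develop AF/AFL during the standard clinical EP study. If it sustains >30 seconds it will be counted toward the primary endpoint". In that case "the research AF induction pacing protocol will not be performed". The threshold is the general one: "Sustained AF/AFL will be defined by a duration of >30 seconds".

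Section 10.0 calls the primary endpoint yes/no AF inducibility after the infusion, then makes it ordinal by induction stage (0, 1 or 2). It moves patients with AFL alone to a secondary analysis. The aim in section 2.0 covers AF and AFL together. Section 10.0 defines no analysis set and gives no rule for withdrawn patients.

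**The concern.** The trial asks whether the drugs suppress AF. A rule that can remove a dosed patient because AF appeared selects on a post-randomization event close to the endpoint. Double-blinding limits selective decisions by arm. It does not stop AF from occurring at different rates by arm, which is the kind of effect under study.

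The scoring is also open. AF during the EP study counts toward the endpoint, yet such a patient has no Step 1 or Step 2 result. A flutter-only patient counts under section 6.0 and is left out under section 10.0. Section 10.0 reports an interim P-value of 0.075 for a new ordinal endpoint, reviewed in March 2019. Scoring choices left open until after that look are hard to defend unless they are fixed blind to arm and dated.

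**Working it through.** **1. The time without a scoring rule.** From Table 3: 1:20 − 0:55 = 25 minutes from infusion start, and 1:20 − 1:05 = 15 minutes from infusion end. The second figure matches the 15-minute wait in section 6.0. The eligibility rule on presenting in AF/AFL that morning does not cover this time.

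**2. The overlap between the two rules.** Rule iv needs spontaneous AF; AF set off by EP-study pacing is not spontaneous. Only unprovoked AF during the EP study meets both rules. The slot is 5 minutes (300 s), and section 6.0 allows up to 96 + 125 = 221 s for pacing. If pacing takes that long, 300 − 221 = 79 s remain for blood draw, TEE and EP study together. The overlap is real but narrow.

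**3. The ordinal scale.** Stages 1 and 2 correspond to Steps 1 and 2 of pacing. Stage 0 most naturally means not induced. AF during the EP study then has no level.

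**4. Bounds without an assumed rate.** The arms are 108 + 108 + 27 = 243. With kS and kR dosed patients lacking an outcome, the worst-to-best range of the S − R difference widens by (kS + kR)/108. One patient gives 1/108 = 0.93 points, 3 give 2.8, and 8 give 7.4. This is a range, not a bias.

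**5. Illustration of selection.** All rates and the correlation are assumptions. Let p be pacing inducibility, s the rate of spontaneous AF before testing, and J the probability of both, from two standard normals with correlation ρ.
- Left out: rate = (p − J)/(1 − s).
- Counted as an event: rate = p + s − J.

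The target is inducibility in all dosed patients: S 55% v R 45%, 10.0 points.

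Example, ρ = 0.5, 5% v 3%, left out: S (0.55 − 0.0452)/0.95 = 53.1%; R (0.45 − 0.0262)/0.97 = 43.7%; difference 9.4.

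| Spontaneous AF, S v R (ρ = 0.5) | Left out | Counted as event |
|---|---|---|
| 2% v 1% | 9.7 | 10.0 |
| 5% v 3% | 9.4 | 10.1 |
| 10% v 5% | 8.5 | 10.5 |
| 15% v 5% | 6.9 | 11.6 |
| 10% v 10% | 10.3 | 9.3 |
| 5% v 10% | 12.0 | 8.5 |

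At ρ = 0, leaving patients out causes no bias at any rate. At ρ = 0.8 the left-out column becomes 9.6, 9.3, 8.0, 5.3, 10.9 and 13.5.

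**6. Counting has its own cost.** Take equal inducibility (50% v 50%), 15% v 5% and ρ = 0.5. Counting gives S 0.50 + 0.15 − 0.1212 = 52.9% and R 0.50 + 0.05 − 0.0439 = 50.6%, so 2.3 points appear where pacing inducibility does not differ. Leaving out gives S (0.50 − 0.1212)/0.85 = 44.6% and R (0.50 − 0.0439)/0.95 = 48.0%, or −3.4 points. Neither rule is neutral.

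**The case against.** Rule iv has a sensible purpose. The endpoint is inducibility by pacing, and a patient already in AF cannot be tested for it. Leaving such a patient out is defensible for a mechanistic trial, and counting spontaneous AF as an event answers a different question. That stands, and it is why the choice should be stated and the result shown both ways.

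The numerical case is also thin. The window is short, patients presenting in AF/AFL are excluded, and the larger shifts need an assumed 15% v 5% split. That stands too.

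A reader might infer more than the documents support:
- That AF events are in fact being discarded by arm. Withdrawal is discretionary, the trial is double-blind, and no count of such withdrawals is given.
- That the data of these patients are destroyed. The sentence belongs to withdrawal of consent, and nothing extends it to PI withdrawals, although nothing rules that out.
- That section 9.0 contradicts section 6.0 outright. They meet only for unprovoked AF during the EP study.

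What the objection does not answer is that rule iv has no lower time limit, that no analysis set is defined, and that AF which section 6.0 does count has no clear ordinal level.

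**Conclusion.** The point holds as a gap in the analysis rules that should be closed; it is not a demonstrated bias. As written, dosed patients can leave the primary analysis because of a post-randomization rhythm close to the endpoint, AF during the EP study has no clear level, and the AFL rule differs between sections.

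Size and direction are unknown, because no spontaneous-AF rate is given. At assumed rates of 2% v 1% or 5% v 3% and ρ = 0.5, a 10.0-point difference becomes 9.7 or 9.4. Larger imbalances can move it either way (6.9 to 12.0 in the cases shown). If spontaneous AF is unrelated to inducibility, leaving patients out does not bias the comparison. It does not follow that the R v S comparison is invalid, or that all AF after dosing must be counted as an event.

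**What to change.** Change the analysis text in sections 2.0, 6.0, 9.0 and 10.0, with no change to clinical management.

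1. For analysis, let rule iv remove a patient only if AF, AT or AFL starts before the infusion. Randomized, dosed patients otherwise stay in the analysis set, except where consent is withdrawn and data must be destroyed. State whether the destruction sentence applies only to that case.
2. State that the section 6.0 rule prevails over rule iv for AF over 30 seconds during the EP study. Define Stage 0 and give this AF an ordinal level, fixed blind to arm.
3. For AF over 30 seconds that starts after infusion start and before the EP study, fix one primary scoring blind to arm. Report the result both ways: counted as an event, and left out as untestable. Say that counting it changes the estimand from pacing inducibility to any AF after dosing. Say also how a patient is scored whose AF stops and who is then paced.
4. Make the AFL-only rule the same in sections 2.0, 6.0 and 10.0.
5. Report dosed withdrawals by arm and by reason i to iv, with an all-induced/none-induced bounding analysis where no outcome exists. Date the change relative to the March 2019 interim look.

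The cost is a little more analysis work, with no added procedures. The downside is that, depending on the scoring chosen, the endpoint may include some AF that pacing did not induce.
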